3 STATISTICAL PRINCIPLES

Statistical analyses will be carried out by the study biostatistics team within the Louisiana Clinical and Translational Science (LA CaTS) biostatistical core under supervision of the principal statistician [name], who also developed the statistical analysis plan. Analyses will use R (version 4.3.1). The primary methodology will be linear models and linear mixed-effects models to account for within-person correlations arising from repeated measures over time. Further details about the covariance structures are described below. Results will be given in the form of within- and between-group effect estimates derived from the model, as applicable. Unless otherwise stated, significance will be set at alpha ≤0.05. No adjustments for multiplicity will be performed for secondary and exploratory outcomes; these results will be reported as point estimates with corresponding 95% confidence intervals that will not be adjusted for multiplicity. We will highlight that caution is warranted in interpreting these effects and the results should not be used to infer definitive treatment effects.

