2.2. Endpoints

Primary endpoint:

• Incidence of appropriate weight gain in pregnancy as defined by the 2009 IOM Guidelines [2].

Secondary endpoints:

- Rate of GWG per week
- Maternal diet (24h recall)
- Physical activity (Accelerometry, Pregnancy Physical Activity Questionnaire)
- Quality of life and stress (Depression Anxiety Stress Scales-21, Quality of Life Inventory, Household Chaos Questionnaire)
- Maternal and infant birth outcomes
- Infant feeding style (Infant Feeding Style questionnaire and Breastfeeding Questionnaire)
- WIC food voucher redemption rate
- Postpartum weight retention (measured 1, 6 and 12 months after delivery)

Exploratory endpoints: This study is also powered for a comparison of GWG between BMI categories. As an exploratory aim we will test whether maternal body mass index (BMI) is a moderator of intervention effects on GWG (relative to Usual Care).

Planned post-hoc analyses include testing moderators of intervention effects on GWG in BMI categories, race/ethnicity groups and in the SmartMoms[®] group only, intervention adherence.

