1.3 Study Aims and Endpoints

The overarching goal of the study is to test the effectiveness of SmartMoms®, a patient-centred, pragmatic and scalable intensive lifestyle intervention, to foster healthy GWG in low-income pregnant individuals in the WIC program, a health disparate, racially diverse and underserved population.

Hypothesis 1: The incidence of appropriate study observed GWG per week according to the 2009 Institute of Medicine guidelines [1] will be higher in the SmartMoms® group as compared to the Usual Care group.

Hypothesis 2: Study observed GWG seen in the SmartMoms® group will be less as compared to the Usual Care group. This will be assessed using the following three measures: study observed GWG, weekly GWG, and deviation from the 2009 Institute of Medicine guidelines.¹

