1.5 Exploratory Aims

We designed the research program such that our primary objectives, described above, are the foundation of a rigorously designed study with mechanistic hypotheses. Such a study design requires focus and derivation of hypotheses that are strongly supported by preliminary data and adequate study power. Through this process, we identified many promising hypotheses that did not meet our rigorous criteria for being a primary outcome. Pregnancy and birth outcomes are of great significance but have less supporting evidence and we therefore classified them as exploratory outcomes.

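### The SAP and the protocol disagree on which endpoints are primary, and the SAP's multiplicity rule leaves Hypothesis 2 unclassified

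*SAP*

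**What the plan says.** **Protocol, section 2.2.** There is one primary endpoint: "Incidence of appropriate weight gain in pregnancy as defined by the 2009 IOM Guidelines". The weekly rate of GWG is the first item under secondary endpoints. Total observed gain does not appear by name in the endpoint list. Deviation from the guidelines appears in section 2.1 as Hypothesis B, separate from the incidence hypothesis.

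**SAP, section 1.3.** Hypothesis 1 concerns "The incidence of appropriate study observed GWG per week according to the 2009 Institute of Medicine guidelines". Hypothesis 2 says gain will be less with SmartMoms: "This will be assessed using the following three measures: study observed GWG, weekly GWG, and deviation from the 2009 Institute of Medicine guidelines". Neither hypothesis is ranked above the other.

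**SAP, section 1.5.** Immediately after the aims and subgroups, the text reads "our primary objectives, described above, are the foundation of a rigorously designed study with mechanistic hypotheses". It then classes pregnancy and birth outcomes as exploratory. Section 2 refers to primary outcomes in the plural without listing them.

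**SAP, section 3.** "Unless otherwise stated, significance will be set at alpha ≤0.05". Then: "No adjustments for multiplicity will be performed for secondary and exploratory outcomes"; these are to be reported as estimates with unadjusted 95% intervals, with a statement that "caution is warranted in interpreting these effects and the results should not be used to infer definitive treatment effects". The current SAP assigns no outcome to the secondary class and gives no testing order, gatekeeping or alpha split.

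**The concern.** The Section 3 rule is a reasonable safeguard, but it works only if the reader can tell which outcomes it covers. On the SAP's wording there appear to be two tiers, primary objectives and exploratory outcomes, with the three Hypothesis 2 measures in the first. On the protocol's wording there is one primary endpoint, and weekly gain sits below it.

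The two readings matter most if the incidence of appropriate gain shows no difference but total or weekly gain does. Under the protocol, that is a null primary result with a supportive secondary finding. Under a literal reading of SAP 1.3, 1.5 and 3, it could be reported as a primary objective met at 0.05. As nothing in the SAP settles the matter, the choice could be made after the results are known.

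**Working it through.** **1. The plan's own figure.** The documents state no familywise error rate. The related stated figure is N=330, which SAP 2.3.1 derives from Hypothesis 1 alone: 28.7% against 44.7%, 80% power, alpha 0.05, 1:1 allocation, 15% attrition.

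- n per arm = [1.96·√(2·0.367·0.633) + 0.8416·√(0.287·0.713 + 0.447·0.553)]² / 0.16²
- = [1.96·0.6816 + 0.8416·0.6722]² / 0.0256 = 1.9017² / 0.0256 = 141.3, so 142.
- Total 284; 284/0.85 = 334.1, so 335. The stated 330 is within 2% of this.

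N therefore matches one two-sided test at 0.05, with no alpha reserved for Hypothesis 2. Expected number analysed: 330 × 0.85 ≈ 280.

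**2. Benchmarks for independent tests**, 1 − 0.95^k for either direction and 1 − 0.975^k for benefit only:

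| Tests | Either direction | Benefit only |
|---|---|---|
| 1 | 5.0% | 2.5% |
| 3 | 14.3% | 7.3% |
| 4 | 18.5% | 9.6% |

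The four measures are not independent. Under SAP 4.2, weekly gain is observed gain divided by the weeks between visits, so those two tests nearly coincide.

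**3. Simulation under no effect.** From the documents: about 280 analysed, three equal BMI strata, 1:1 allocation within each, the SAP Table 4 bounds, and deviation analysed only in women outside the bounds. Linear comparisons were adjusted for BMI category; incidence used a BMI-stratified score test in place of the logistic model.

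Assumed: normally distributed weekly gain, about 22 weeks between visits, and the SD and mean. The documents do not give the last two for this population, so a range was used:

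- The upper SD comes from solving SAP 2.3.1's claim of 80% power for 0.16 kg/week within a BMI category: 110 × 0.85/2 = 46.75 per arm, SD = 0.16 / [2.8016·√(2/46.75)] = 0.276.
- The lower SD, 0.15, with a mean 0.05 above mid-range puts 28.6% of women in range, close to the SAP's 28.7% for Usual Care.

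Results with 10,000 replicates per setting (Monte Carlo standard error about 0.35 points in the third column):

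| SD (kg/week) | Mean above mid-range (kg/week) | Any of four, p<0.05 | Any of four, in favour of SmartMoms |
|---|---|---|---|
| 0.15 | 0 / 0.05 / 0.10 | 15.6 / 14.7 / 13.3% | 8.0 / 7.4 / 6.5% |
| 0.20 | 0 / 0.05 / 0.10 | 14.6 / 13.9 / 13.8% | 7.6 / 7.4 / 7.0% |
| 0.276 | 0 / 0.05 / 0.10 | 14.8 / 14.1 / 13.7% | 7.4 / 7.1 / 6.8% |

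The test statistics for observed and weekly gain correlate at 0.98–1.00, so four measures behave like about three tests. The chance that a Hypothesis 2 measure is significant while Hypothesis 1 is not is 8.5–10.4% in either direction, and 4.0–5.3% counting benefit only. Moving the mean to 0.2 above mid-range (SD 0.20), near the pilot's Usual Care deviation of 0.208 in overweight women, lowers the third column to 12.6–12.9%.

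**4. The other reading.** If Hypothesis 2 is secondary, one primary test remains at 0.05: 5% for either direction, 2.5% for benefit.

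**The case against.** The strongest reply is that Hypothesis 2 was never meant to be primary. No passage names any of its measures as a primary outcome. The protocol lists weekly gain as secondary. The SAP's amendment log describes the change to section 1.3 as a clarification of wording and records no promotion of Hypothesis 2. The sample size rests on Hypothesis 1, while Hypothesis 2 only gets a power statement at that size. And if Hypothesis 2 were primary, the word secondary in Section 3 would refer to nothing. Reading it as secondary agrees with the protocol and gives the rule content.

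Most of this stands. It makes the secondary reading the more natural one, and it means that 13–15% cannot be called the trial's error rate. It does not remove the conflict: section 1.5 calls the objectives above it primary, and section 1.3 holds both hypotheses.

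It is also fair to object that both hypotheses are directional, so the either-direction figure includes results showing SmartMoms to be worse. That stands too. The benefit-only figure of about 7% is the one to set against a claim of success, and it is still nearly three times the 2.5% of a single two-sided test.

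A reader might go further and add the 12 BMI-category tests (four measures in three strata), for a total near 40%. The documents do not support this as an error rate for a primary claim. SAP 1.4 calls these subgroup analyses, and nothing lets a stratum result establish success.

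**Conclusion.** The concern holds as a conflict between the documents over endpoint hierarchy. The protocol has one primary endpoint; the SAP presents two unranked hypotheses as primary objectives, tests everything at 0.05, and attaches its caution to a secondary class with no members.

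The consequence is conditional. If both hypotheses are primary, the chance under no effect of at least one two-sided p<0.05 among the four overall measures is about 13–15% (one simulated setting reached 15.6%), against 5%; a false claim of benefit is about 7%, against 2.5%. Both figures rest on about 280 women analysed and on the assumed SD (0.15–0.28 kg/week) and mean (0–0.1 kg/week above mid-range). If Hypothesis 2 is secondary, the primary error is 5%.

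A reader might infer that the SAP makes Hypothesis 2 primary outright and that the trial therefore carries a 14% error rate. The text does not say so; it leaves the choice open. That still warrants correction, because it determines what the trial may claim if incidence is null.

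**What to change.** In SAP 1.3 and 1.5, state that Hypothesis 1 in the whole sample is the only primary test, at 0.05, as in the protocol. Label the three Hypothesis 2 measures secondary, and state that the BMI-category analyses are subgroup analyses. Put both under the existing Section 3 rule: estimates with 95% intervals and no definitive inference. If results are already available, apply the protocol's hierarchy in reporting them.

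The cost is about two sentences. No analysis changes, and N=330 is unaffected because it was derived from Hypothesis 1 alone. The downside is that Hypothesis 2 alone can no longer support a confirmatory claim.

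Keeping all four measures primary would cost more. Bonferroni gives 0.05/4 = 0.0125 each, and power for Hypothesis 1 with about 280 analysed (140.25 per arm) falls from 79.7% to about 61%: (0.16·√140.25 − 2.498·0.6816)/0.6722 = 0.286, and Φ(0.286) = 0.61.

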3.1 Distributional assumptions

Preliminary statistical testing will be performed to investigate homoscedasticity and normality of model residuals. Visual inspections will initially be performed, followed by more tests when departures from normality are present.

3.2 Covariance structures

The variance-covariance structure of the repeated effects will be dependent on the variability among all participants. A preliminary test will be conducted to assess significance of the homogeneity of variances for between-group differences. The within-participant variability will be modelled with an unstructured covariance matrix. Correlation patterns will be assessed with Akaike's Information Criterion (AIC) to make final selections.

3.3 Covariates

The models will include the following covariates: gestational age at randomization, BMI category at randomization, and parity defined categorically as nulliparous vs non-nulliparous.

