12.3. Data Analysis Plan

Statistical analyses will be completed using SAS/STAT[®] software, Version 9.4 of the SAS System for Windows (Cary, NC, USA) by a Biostatistician. All tests will be performed with significance level α =0.05 and using intent-to-treat analysis. Outcomes will be assessed for normality (where appropriate) with the Shapiro-Wilk test. If transformed data is still not normally distributed, then non-parametric analyses will be conducted on these outcomes. LARS (least-angle regression) will be used for the covariate selection methodology. Covariates will include, but may not be limited to, the infant sex, gestational age at delivery as well as and the maternal age, weight at screening, parity, race/ethnicity, and gestational diabetes status. Treatment and BMI category will be included in all models. Intent to treat analysis will be the primary analysis type. Both completers and multiple imputation (Markov chain Monte Carlo method, preferred) may also be performed if there is a large amount (>10%) of missing data. However, we will extract the mothers' WIC record and therefore for participants who fail to return to clinic, weight measurements will be acquired from the planned chart abstraction. This should greatly decrease the amount of missing data from loss to follow-up.

Hypothesis A: Higher incidence rate of appropriate GWG

Initial results will be expressed contingency tables with incidence rate and either treatment or BMI category. Tests for associations between these variables will be based on Pearson's Chi-squared statistic. Further results will be based on a generalized linear mixed effect model with a binary distribution and a log odd link function modeling the incidence rates. The model will use random effects to account for a site effect and within-subject correlation over time. Results from this model will be reported as odds ratios of least square means, with p-values based on z-tests. Two different sets of models will be used. The first set of models will contain only treatment and BMI category, while the second is will also contain the covariates based on LARS. Pairwise post-hoc comparisons of the category variables will be corrected for multiple comparisons will be made when necessary.

Hypothesis B: Small Deviation in Weekly GWG

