Overall deviation rates will be reported using a linear effect mixed model, using random effects to account for site and within-subject correlation. The response is the deviation of the weekly GWG rates from the IOM guideline rates. Models will be reported using both the simple model with treatment and BMI category and with covariates selected by LARS. Adjusted means of the deviations will be obtained using the least squared means. Two-sample t-test will be used to compare adjusted mean deviations.

Hypothesis C: Improvements in Physiological and Behavioral Factors

Each physiological and behavioral factor will be investigated independently from each other. Linear mixed effect models, like the ones listed in 2B, will be used to test differences between the treatment groups with least square

means. The response for each of these models will include both repeated measures and percent change from baseline approaches.

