The sample size was changed to enroll at least 330. The COVID-19 pandemic occurred in the early stages of data collection for the trial (i.e., 9 months after the first participants was screened). This resulted in several statewide restrictions, including lockdowns (with the initial "Stay at Home Order" issued on March 22nd, 2020), after 87 participants had been screened and 26 participants were in the primary data collection phase of the trial. Study visits were continued for participants who were already in the screening process or enrolled in the trial. It was necessary for visits to be modified to allow for collection of data to occur in a manner that ensured compliance with COVID-19 mandates (e.g., social distancing, wearing of PPE, etc.) for the participant and study staff. Restrictions required recruitment to cease for 5 months (March 2020 through July 2020). Research activities resumed when Louisiana progressed to Phase 2 of the reopening plan however, multiple restrictions were still in place that required adjustment of study procedures (detailed in the amended protocol). To adjust to and address the unforeseen circumstances arising from COVID-19 (including to comply with the time constraints set by the funding institute), the trial steering committee decided in October 2022 to end enrolment by December 2023. Based on trial enrolment through 2022, enrolment rate was estimated to be at least 11 participants per month for the following year, and as a result, it was assumed that the trial could achieve a sample size range of between N=339 and N=360. See below in section 2.3 for more details.

Section 2.2

Amendment May 2024:

The randomization section edited to denote that regions were used as the blocking information for the randomization scheme as compared to clinics since multiple clinics per regions were used for enrolment.

Section 2.3

Amendment October 2022:

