The sample size was updated to a minimum of 330. The initial estimated effect size for the SmartMoms® intervention was based on preliminary data in the Expecting Success trial. The incidence of appropriate GWG for people with overweight was 12.3% for Usual Care versus 43.8% in SmartMoms®, and in people with obesity, it was 0% for Usual Care and 42.9% in SmartMoms®. However, the Expecting Success trial was not conducted in an exclusively underserved population, so we needed to conservatively estimate the SmartMoms® intervention effect to ensure this study would be well powered. The incidence of appropriate GWG for the Usual Care group was derived from individuals receiving WIC benefits in the 2013 Louisiana Pregnancy Risk Assessment Monitoring System data. The table below was created to show the incidences needed for 80% power in each of the BMI categories. All the estimates were tenable since they were lower than the SmartMoms® trial estimates. This study aimed for a total sample of 432 originally to allow for unknown variability that may have caused the observed rates to be different than the ones used for the power analysis. Sample size was reassessed in response to the COVID-19 pandemic. Based on the feasible recruitment estimates, the sample size was lowered to a minimum of 330. No new data were used to obtain the changes in power.

Table 1. Sample Size Estimates

BMI Category	Usual Care Appropriate GWG Incidence Rate	SmartMoms® Appropriate GWG Incidence Rate				
Normalweight	36.9	50.9	51.4	51.9	52.4	52.9
Overweight	23.9	37.9	38.4	38.9	39.4	39.9
Obesity	25.2	39.2	39.7	40.2	40.7	41.2
Overall	28.7	42.7	43.2	43.7	44.2	44.7
Sample Size		432	405	372	350	330

Section 3.0

Amendment May 2024:

Section was rewritten to clarify that treatment group differences within each BMI category is an apriori subgroup analysis we would consider.

Section 3.1

Amendment May 2024:

Description of methodology used to assess distributional assumptions was reduced to allow for which test is most statistically appropriate to be used.

Section 3.3

Amendment May 2024:

Based on recommendation from other statistical analysis experts in maternal health, a priori variable selection for determining covariates will be used. Gestational age at randomization, BMI category at randomization, and categorically defined parity will be the only covariates to be included in the model. Exploratory analysis will examine relationships of the outcomes with other

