2.2 Randomization

Individuals will be randomized 1:1 to either the SmartMoms® or Usual Care group. Prior to randomization, the participant and study staff will review a document that outlines behavioral requirements for each group and affirms responsibilities during the study. Once the participant confirms understanding of study requirements, randomization will occur via a phone call with intervention staff. The randomization schedule will be prepared by the study statistician and use a permuted block strategy with stratification for LDH region (1 through 9) and BMI category (normal weight, overweight, obesity) to ensure balance within each stratum between individuals in the SmartMoms® or Usual Care groups. The Research Electronic Data Capture (REDCap) will be used to conceal the allocation sequence to intervention staff until randomization occurs.

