4.3 Analyses of Study Aims

Hypothesis 1: The incidence of appropriate study observed GWG per week according to the 2009 Institute of Medicine guidelines¹ will be higher in the SmartMoms® group as compared to the Usual Care group.

The categorical outcome of study-observed GWG per week attainment will be analyzed using a general linear model with a fixed effect for group (SmartMoms®, Usual Care) with a binary distribution and a log odd link function modeling the incidence rates. Covariates will include BMI category (normal weight, overweight, obesity) at randomization, parity (nulliparous, non-nulliparous), and gestational age at randomization. Results will be reported as adjusted odds ratios (OR) and/or relative risks (RR) as appropriate. The analysis will also be conducted and reported within each BMI category.

Hypothesis 2: Study observed GWG seen in the SmartMoms® group will be less as compared to the Usual Care group. This will be assessed using the following three measures: study observed GWG, weekly GWG, and deviation from the 2009 Institute of Medicine guidelines.¹

The continuous outcome of study observed GWG will be analyzed using a linear mixed-effects model including fixed effects for time (early pregnancy, late pregnancy), group, and the interaction thereof, with participant as a random effect to account for within-participant repeated measures as well as BMI category (normal weight, overweight, obesity) at randomization, parity (nulliparous, non-nulliparous), and gestational age at randomization as covariates. The continuous outcomes related to study observed GWG per week assessed only during late pregnancy (i.e., weekly GWG and deviation from the 2009 Institute of Medicine guidelines) will be analyzed analogously using a linear model with a fixed effect for group and the same covariates. The analysis will also be conducted and reported within each BMI category.

Exploratory: The incidence of adverse perinatal outcomes will be less in the SmartMoms® group as compared to the Usual Care group.

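### LDH region stratifies the randomization but is in no SAP model, and the covariates in the study observed GWG mixed model do not adjust the gain

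*SAP*

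**What the plan says.** **Randomization.** SAP 2.2 will "use a permuted block strategy with stratification for LDH region (1 through 9) and BMI category", that is 9 × 3 = 27 strata. The amendment list at the front of the SAP (entry for Section 2.2) agrees that "regions were used as the blocking information for the randomization scheme as compared to clinics".

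**Covariates.** SAP 3.3 reads: "The models will include the following covariates: gestational age at randomization, BMI category at randomization, and parity defined categorically as nulliparous vs non-nulliparous". The amendment entry for Section 3.3 closes the list: gestational age, BMI category and "categorically defined parity will be the only covariates to be included in the model". The Hypothesis 1, Hypothesis 2 and exploratory models in SAP 4.3 use these three and nothing else.

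**Protocol.** Protocol 12.3 included site. For Hypothesis A, "The model will use random effects to account for a site effect and within-subject correlation over time"; for Hypothesis B, a mixed model "using random effects to account for site and within-subject correlation".

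**Study observed GWG.** SAP 4.3 fits a mixed model with time (early, late), group and their interaction, "with participant as a random effect to account for within-participant repeated measures as well as BMI category", parity and gestational age. No covariate × time term is listed. In the same paragraph, weekly GWG and deviation "will be analyzed analogously using a linear model with a fixed effect for group and the same covariates".

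**The concern.** There are two separate points.

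1. Stratified blocks balance the arms within region. If regions differ in the outcome, that balance lowers the true variance of the treatment comparison, but a model without region does not credit it. The reported standard error is then slightly too large and some power is lost. The SAP adjusts for one of its two stratification factors and not the other, and does not say why the site effect was dropped.

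2. Study observed GWG is late minus early weight. A covariate entered only as a main effect shifts both weights of a woman equally, so it says nothing about her gain. The result would be taken as adjusted in the same way as weekly GWG beside it, but it is essentially the raw difference in mean gain.

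Precision and accurate description are at stake. Bias and false positives are not.

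**Working it through.** **The plan's own N.** For 28.7% vs 44.7% (SAP Table 1), two-sided α = 0.05, power 80%, pooled variance and no continuity correction: 142 per arm, 284 in total. Dividing by 0.85 gives 335 and multiplying by 1.15 gives 327, so the stated 330 is reproduced and is not in dispute.

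**Region, Hypothesis 1.** From the SAP: N = 330, 15% loss, Table 1 Usual Care rates, +16 points, 9 regions × 3 BMI strata. Assumed: equal regions, blocks of 4, and the between-region SD of log-odds, which neither document gives. Each simulated trial was analysed with the SAP's logistic model without region, with a random region intercept, and with fixed region. Entries are percentages in that order.

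| Region SD | Held fixed | Power | Type I error |
|---|---|---|---|
| 0 | overall rates | 80.6 / 80.6 / 80.9 | 5.2 / 5.3 / 5.5 |
| 0.3 | overall rates | 81.0 / 81.3 / 81.9 | 4.5 / 4.6 / 5.0 |
| 0.5 | overall rates | 80.9 / 81.9 / 82.6 | 4.7 / 5.0 / 5.4 |
| 0.7 | overall rates | 81.6 / 83.7 / 84.5 | 4.7 / 5.5 / 5.7 |
| 0.5 | within-region odds ratio | 76.5 / 78.0 / 78.8 | 4.7 / 4.9 / 5.3 |
| 0.7 | within-region odds ratio | 73.8 / 77.0 / 77.8 | 4.1 / 4.9 / 5.3 |

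There were 10,000 trials per setting with overall rates fixed; with the odds ratio fixed, 6,000 for power and 5,000 for type I error. The power gain from adding region is therefore 0 to 0.3 points at SD 0, 0.3 to 0.9 at 0.3, 1.0 to 2.3 at 0.5 and 2.1 to 4.0 at 0.7. The upper ends belong to fixed region and partly reflect its Wald test being slightly anti-conservative. With unequal regions (5 to 20% each, SD 0.5) power was 80.1 / 81.2 / 81.9.

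**Study observed GWG, algebra.** The SAP model for woman i at time t (0 early, 1 late) is

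Y_it = α + βt + γG_i + δ·t·G_i + X_i′θ + b_i + e_it.

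Subtracting, D_i = Y_i1 − Y_i0 = β + δG_i + (e_i1 − e_i0). The covariates X_i and the random effect b_i are gone. The remaining information, early weight given D_i, has its own free intercept, group and covariate coefficients, so it carries nothing about δ. This also holds under the unstructured covariance of SAP 3.2. With complete pairs, the estimate of δ is the raw difference in mean gain.

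**Numerical checks on simulated data.**
- 330 complete pairs: time × group = −0.5269, SE 0.5434, with and without the covariates, and equal to the raw difference. Unstructured covariance gives the same estimate. Covariate × time terms, or regressing gain on group and covariates, give −0.5138, SE 0.503.
- 279 complete pairs: −1.849, SE 0.821, with and without main-effect covariates; −2.024, SE 0.780, with covariate × time.
- About 16% of late weights removed: the main-effect covariates now enter through women with only an early weight, but the estimate is −1.039 against a raw completers' difference of −0.994, a shift of 0.045 kg beside an SE of 0.58.

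**Why gain depends on the covariates.** SAP Table 4 midpoints are 0.425 kg/week (normal weight) and 0.22 (obesity). Over about 23 weeks that is 0.205 × 23 = 4.7 kg. The visit windows in SAP 2 allow intervals from 35w0d − 16w6d = 18w1d to 37w6d − 10w0d = 27w6d.

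**Size.** The documents give no SD for weekly gain, so it was backed out of the stated power with SD = difference / [(1.96 + 0.842)·√(2/n per arm)].
- SAP: 0.16 kg/week, n = 110 × 0.85 / 2 = 46.75, giving SD 0.276.
- Protocol: 0.12 kg/week, n = 144 × 0.85 / 2 = 61.2, giving SD 0.237.

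With 330 × 0.85 / 2 = 140.25 per arm, and mean rates assumed at the Table 4 midpoints + 0.06 to + 0.21 kg/week, 3,000 simulations per SD gave:

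| Weekly SD | SE as planned (kg) | SE with covariates acting on gain (kg) | Power at 0.08 kg/week |
|---|---|---|---|
| 0.276 | 0.80–0.81 | 0.76–0.77 | 64% → 68% |
| 0.237 | 0.70–0.71 | 0.66 | 75% → 78–80% |

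The SE ratio is 0.930 to 0.953, an effective sample-size ratio of 1/0.953² = 1.10 to 1/0.930² = 1.16. At the SAP's 0.16 kg/week, overall power is 99.7% or more either way. Within one BMI category the SE ratio is 0.99 to 1.00.

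**The case against.** The strongest case is that this is precision only, and little of it. The one spread of rates in the documents is across BMI categories: Table 1 Usual Care log-odds of −0.54, −1.16 and −1.09 have an SD of about 0.3. A region SD of 0.7 would let rates within one state program run from about 9% to 62% (28.7% ± 2 SD on the log-odds scale). At SD 0.3 a random intercept moves power only from 81.0 to 81.3%. That stands as a reason to expect the lower end of the range, though it does not show that regions are alike.

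Three further points stand in part:
- The protocol does not define site as LDH region, and the SAP distinguishes regions from clinics. A region intercept follows the protocol's intent and the SAP's stratification, not the protocol's exact term.
- The amendment does give a reason for the closed list: a priori selection on expert advice. It explains dropping variable selection, but not dropping site.
- Weekly GWG uses the same two weights and is properly adjusted, and the raw gain contrast is a valid comparison because randomization balances BMI category. The 0.08 kg/week in the power illustration is half the SAP's figure and was chosen for this check.

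None of this puts region into a model or makes the listed covariates adjust the gain.

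**Conclusion.** Both points hold, and the change should be made, but neither endangers the trial. Leaving region out of Hypothesis 1 is harmless if regions are alike and costs about 2 to 4 power points if they differ strongly (SD 0.7). At SD 0.3 the loss is under 1 point. These sizes rest on the assumed region SD and block size, and the SD 0.3 figure was computed only with overall rates held fixed. Type I error without region was 4.1 to 5.2%, so any conservatism is slight.

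The cancellation in the study observed GWG model is exact for women with both weights and needs no assumption. Its cost, a standard error 5 to 7% smaller if the covariates acted on gain, depends on the SDs implied by the stated power and on the assumed mean rates. It affects only this one of the three Hypothesis 2 measures; Hypothesis 1, weekly GWG and deviation do adjust with their covariates.

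**What to change.** 1. In SAP 3.3 and 4.3, add LDH region to the full-sample Hypothesis 1 and Hypothesis 2 models, preferably as a random intercept, otherwise as a fixed effect. If region is left out on purpose, state the reason.
2. In the within-BMI models and for rare exploratory outcomes, use a random intercept or omit region. In a simulated overweight stratum (SD 0.3), fixed region gave type I error 6.6%, against 5.4% without region and 5.8% with a random intercept, and 59% of trials had a region with all or no events. For an outcome at an assumed 8% rate, 64% of full-sample trials did.
3. For study observed GWG, regress late-minus-early gain on group, the three covariates and region, or add covariate × time terms to the mixed model. Region entered there only as a main effect or random intercept would cancel too.

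Cost: SAP wording. Region is known for every woman and N does not change. Fixed region uses up to 8 degrees of freedom and makes the Wald test slightly anti-conservative; full-sample and subgroup models may differ in how they treat region. The SAP was finalized in May 2024, after the planned end of enrolment, so the change needs a dated amendment made without sight of outcomes by arm. If that is no longer possible, report the revised models as labelled sensitivity analyses.
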